- Patients and Family Members/Friends: We will minimize this potential risk by being very clear that participation is completely voluntary, that withdrawal is always possible during the trial, and that usual clinical care will not be impacted by the decision to participate or not to participate in the clinical trial. Treating clinicians will not be involved in the consenting of patients and thus will not be in a position to coerce participants; recruitment will be performed by study staff. Additionally, study staff will encourage patients to have a family member or friend present for the consent procedure (especially as we will be recruiting one family member or friend per participant). There will be no exchange of payment for study participant referrals. The clear alternative to participation in the trial will be usual clinical care. Because research staff will be assessing patients current suicidality through the use of the C-SSRS, the potential for both patient participants as well as family/friend participants to be unclear on the roles of researchers versus their treating providers. Research staff will make clear their roles as researchers versus clinical staff during the consent process, specifically noting that decision to participate will not impact their clinical care.
- ED Providers: A study staff member without a clinical relationship to the ED or to the ED providers will be the only one aware of which providers have completed surveys ED.

Loss of confidentiality (all participants): Loss of confidentiality is a potential serious risk. We will be diligent in safeguarding protected health and other participant information in the collection, processing, and storage of information, and all the data generated by the study will be kept strictly confidential. No reports will be released containing protected health information or other identifiers that would allow a study participant to be identified. Individual participant contact information will be collected at the time of enrollment (prior to randomization) and this information will be kept in a secure, locked file cabinet in the Department of Emergency Medicine offices and in password protected, secure electronic files. Participants will not be identified by name or medical record number on any of the data forms or specimens except the initial enrollment and consent forms. Other paper and electronic data will be made anonymous using unique identification codes and participant initials. Electronic files will be stored on password protected computers, or REDCap, behind the University of Colorado Denver firewall.

Worry about firearm confiscation

- Patients and family members/friends: We recognize that participants may view this as a study risk, although it is not actually one. Specifically, some may fear that, if they reveal they have firearms at home, legal authorities will confiscate them. We will explain to every participant that study staff will not enter information about firearm access into the medical record, nor will they disclose access to any legal authorities. We will also not ask about how firearms were acquired (i.e., whether they were legally-purchased or transferred).

[figure not shown]
Should staff have concern about a participant's imminent safety, they would follow study protocols to notify clinical staff in the ED or connect the patient with a suicide hotline. While clinical staff may document firearm access, as they might during typical care, we will reassure participants that such information is not shared with legal authorities unless an individual is specifically threatening harm towards specific individuals (as per required reporting under the *Tarasoff* decision).

Language: As this is currently a small pilot trial, the LM-DA will not be translated into Spanish or other languages at this time. However, if analyses indicate a larger scale trial is indicated, the LM-DA would be translated into Spanish for larger scale testing.

E. Potential Scientific Problems: Identification of eligible patients and review of records could be difficult, given the high volume of patients seen in the complex EDs included in this study. However, all three sites use Epic for their electronic medical record system and have Epic-based ED tracking boards that research staff can monitor (as we have done previously in the ED-SAFE studies). Study staff have expertise with using Epic for enrollment and medical record review (at baseline and for later utilization reviews). In addition, all three clinical sites (as well as a number of other Denver-area hospitals) are connected within Epic, such that subsequent visits to any of the linked EDs would be visible to staff. Staff also have experience accessing vital statistics records and we have a strong relationship with the Colorado Department of Public Health and Environment. Another challenge is the sensitivity of disclosing firearm access, as some patients may be hesitant to reveal ownership or home access. During eligibility screening, study staff will first establish rapport, discuss the larger context for the study (improving home safety generally, without reference to firearms), and explain the basic outline of the study (participation requirements and incentive). They will also explain the confidentiality of the study (including that study staff will not record sensitive or identifiable details in the medical record or databases accessible by law enforcement or government agencies). Only then will study staff ask eligibility questions, with the question related to firearms asked last in hopes of maximizing participant comfort and honesty in answering and in participating. Our enrollment estimates are intentionally conservative and take into account the issue of assessing firearm access. An additional challenge is timing of study procedures relative to ED care. Figure 3 displays the different stages of ED care, where broken arrows represent times ranging from minutes to hours. At point A, patients may be intoxicated or otherwise not medically or cognitively able to participate in the LMC or the study. Most suicidal patients speak with a mental health consultant, who is the person most likely to provide LMC. Assessment of lethal means access may occur during the mental health provider's evaluation (between points B and C), but actual LMC is likely to happen during the discharge process (point D). Thus, for this study, RAs will aim to approach patients during the periods represented by points B and C. In surveys and interviews with providers, we will assess how the LM-DA may have affected subsequent LMC or supported antecedent LMC, data which will inform future real-world implementation into clinical practice. The study staff will have work-spaces in or next to the EDs and the support of their site PIs, along with familiarity with ED patient flow. These factors should facilitate enrollment.

Another area of challenge is blinding to treatment arm. RAs will carry out all study procedures

Figure 3. Time Spent in ED by a Patient with SI/SA

but cannot feasibly be blinded to study arm, as they will need to ensure the patient can access the LM-DA. To blind patients, we plan to use deception (with IRB approval) in the informed consent process such that patients know

the study is examining ways to enhance safety of suicidal patients but do not know that the LM-DA is the intervention of interest. ED providers will not be blinded to participant study group, as providers may review the LM-DA printed results with patients (as they would in real-world implementation). We will notify providers of the study at the start of enrollment and explain the purpose, with the request that providers continue to provide usual care (with or without LMC, as per their usual practice) for patients in the intervention and control groups. A third challenge is testing the role of family or friends. Not all suicidal patients have someone present with them in the ED, so there will be real-world variability in how family or friends are involved with DA completion. Ideally, the person with decision-making control over firearm storage would be involved, but may not be present with the patient. In the current proposal, we will record how often family or friends are present and are (or are not) the ones with control of firearm storage. We will also record how often they are willing to participate in the study – all of these findings will help lay the groundwork for future study. If we find any aspects of the LM-DA are unacceptable, we will revise those aspects and re-review with stakeholders prior to future implementation. Another limitation is finding differences across sites, but not enough events to adjust for site (with a fixed effect). In this case, given that this is a pilot study, we will use two strategies: (1) ignore site and summarize the overall results, and (2) analyze the results ignoring the site with few events. A future study will allow to account for differences across sites.

F. Data Analysis Plan: We will describe the three sites in terms of patient demographics as well as the primary measure (DCS score <25) using appropriate statistical tests (e.g. anova, chi-square). If no differences are found between the three sites, we will ignore site and compare the proportion of the primary measure in the control and intervention groups as the primary analysis. If differences are found among sites and there are enough events, we will use a logistic regression model with a fixed effect for site and with a treatment indicator as the main predictor. Missing data for the primary measure should be minimal, given that this will be obtained before patients leave the ED. For secondary measures, we will use descriptive statistics including proportions with 95% confidence intervals for knowledge, acceptability and feasibility; whether the criteria in Table 1 have been met will be based on the confidence intervals of the proportions. Keeping in mind factors related to pilot trial feasibility, our target sample size (n=60; 30 LM-DA and 30 control) was chosen to allow detection of a 30% difference between the LM-DA and control arms for the primary measure (DCS score <25; Table 2) While this sample size will not allow for full power to analyze moderators by site (as related to either LM decision or trial feasibility measures), it should generate adequate pilot information concerning site selection for the subsequent trial. Participants and RAs will enter survey data directly into REDCap. Participants completing REDCap surveys will be sent a unique link for participation. For follow-up calls, chart reviews and other documents, RAs will enter data into REDCap or store it on password-protected university servers. We will export data to SAS for analyses.

G. Summarize Knowledge to be Gained: The proposed research will provide the scientific foundation for improvement and examination of real-word implementation of an effective, patient-centered LM-DA in EDs and other settings. A web-based tool offers the potential to significantly enhance current care, decrease real-world access to lethal means of suicide, and thereby decrease short-term risk of suicide.

H. References:

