Knowledge	Questions about suicide and LM	X	X				60% of patients identify firearm access as risk for suicide
Decision conflict	Decisional Conflict Scale (DCS)	X	X				Effect size 0.3-0.4 after intervention (target score <25)
Values concordance	DCS Values Clarity subscale	X					NA (informs next trial)
Behavior intent	Theory of Planned Behavior	X					NA (informs next trial)
SHORT-TERM							
Firearm access	Self-report	X	X				NA (informs next trial)
LONG-TERM							
Suicide attempts, deaths	Self-report C-SSRS (BL, 1 week); medical record review (BL, 1 & 3 months)	X	X	X	X		Able to review records for 85% of participating patients
TRIAL MEASURES							
Feasibility	Eligibility, participation Phone follow-up Suicide outcome ascertainment	X		X	X		>50% participation >75% completion Able to review records for 85% of participating patients
Provider training	Time to complete; user feedback					X	NA (informs next trial)
ADDITIONAL MEASURES							
Demographic and clinical characteristics	Questionnaire, C-SSRS; medical record review	X		X	X		NA (informs next trial)
Healthcare utilization review	Medical record review			X	X		Able to review records for 85% of participating patients

estimates decisional uncertainty through personal perceptions of issues such as uncertainty in choosing options, modifiable factors contributing to uncertainty, and effective decision making (e.g., expressing satisfaction with the choice). The DCS is a 16-item scale (with Likert scale response options) that has high reliability and test-retest correlation (Cronbach's alpha coefficients > 0.78).⁹² In prior work, the DCS has been shown to discriminate between known groups who make or delay decisions (effect size 0.4-0.8).⁹² Scores less than 25 (out of 100 total) are associated with implementing decisions;⁹² we will use this threshold as one criterion for progression to the next trial (Table 1), as [name] has done in other studies.

- **Values Concordance:** We will use the "Values Clarity"⁹² subscale of the DCA to examine how much participants feel their decisions are in line with their values.
- **Behavior Intent:** We will measure self-reported intent to reduce access to firearms, including the chosen option(s) for storage, using a Theory of Planned Behavior questionnaire scale.⁹³

(3) Short-Term Outcome: At phone follow-up, we will assess firearm storage (to identify changes from baseline). This will be a primary measure for the subsequent, larger trial.

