Sample Size: Keeping in mind factors related to pilot trial feasibility, our target sample size ($n=60$; 30 LM-DA and 30 control) was chosen to allow detection of a 35% difference between the LM-DA and control arms for the primary measure (DCS score <25 ; Table 2). In a prior small study, 62% of parents of at-risk youth who received LMC reduced home

Table 5. Sample Size Estimates			
Control	LM-DA	% with DCS <25	Total Detectable sample size
		0.6	64
0.5	0.8	0.3	78
	0.85	0.35	54
	0.9	0.4	40
	0.6	0.3	84
	0.65	0.35	62
	0.7	0.4	48
0.3	0.5	0.3	78
	0.55	0.35	58
80% power, $\alpha=0.05$			

access to firearms, compared to 0% of those who did not receive LMC.⁴⁹ Estimates for the effect of LMC on behavior among adults with suicide risk do not exist, so our assumption of a 35% difference is conservative (prior work with other DAs has found an effect size of 40-80% on DCS between groups⁹²). While this sample size will not allow for full power to analyze moderators by site (as related to either LM decision or trial feasibility measures), it should generate adequate pilot information concerning site selection for the subsequent trial.

B. Description of Population to be Enrolled: We will enroll three populations:

- a. 60 patients seen in the ED for SI/SA
- b. Up to 60 influential adult family members or friends (one per enrolled patient), either in person or by telephone (if not present in the ED; n=60 total). Enrollment of a family member or friend will not be required for a patient to participate.
- c. 100 emergency department providers for surveys and 20 for qualitative interviews (may participate in survey, interview or both)

Table 3. Inclusion/Exclusion Criteria

[figure not shown]
	Inclusion	Exclusion
Patients (n=60)	
 • Being evaluated in the emergency department for SI/SA. • Deemed medically stable by ED physician • Age ≥ 18 years • Able and willing to have telephone follow up at 1 week • Report ≥ 1 firearm at home 	
 • Unable to participate medically or cognitively (e.g. sustained altered level of consciousness, hostility, psychosis, sexual assault victim, severe vomiting or pain) • Currently in legal custody • Live in group home or other supervised custody • Already enrolled
Family member or friend (n=60)	
 • Age ≥ 18 years 	
 • Unable to participate cognitively • Already enrolled • Currently in legal custody

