ED Providers (n=100)	
 • Physicians, physician extenders (i.e., physician assistants or nurse practitioners), nurses, and behavioral health evaluators (e.g., social workers, psychologists, advanced practice nurses) who work in the participating EDs • Cared for ≥ 1 participating patient • Completed current care of participating patient(s) prior to beginning the survey 	
 • Current or former member of the study team (i.e. PI, CO-I, RA)

C. Study Design and Research Methods: In this pilot randomized controlled trial, we will test the LM-DA in a sample of 60 adult patients being evaluated for suicide risk at three large hospital EDs. Thirty nine patients will be randomized to the LM-DA group, while 21 will be randomized to the control group (13/7 at each site). Figure 2 displays the overall study flow. Analysis and reporting will follow CONSORT guidelines, and we will register the trial on clinicaltrials.gov. Family member or friends who are concurrently enrolled will also be enrolled in the ED, in the same randomization group as the patient. ED Providers will be surveyed separately.

Study Sites: To prepare for the subsequent multi-site trial, including by identification of moderators of LM-DA and study feasibility at different sites, the pilot will recruit patients, family members/friends, and providers from the EDs at three large, diverse Colorado Hospitals: (1) University of Colorado Hospital (tertiary care center without dedicated psychiatric ED; suburban Denver; part of UCHealth consortium); (2) Memorial Hospital

(hospital with dedicated psychiatric ED; draws from large catchment area in southern Colorado, including rural and urban populations; high firearm ownership rate; part of UCHealth consortium); and (3) Denver Health Medical Center.

Figure 2. General Study Flow

Enrollment:

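### The same 60 patients are said to detect 35 points in one section and 30 in another; the protocol's own table fits only 35, and neither the 39/21 split nor the word 'conservative' is supported

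*Combined protocol and SAP*

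**What the plan says.** The primary measure is the proportion of patients with a DCS score below 25, and the primary analysis compares it between the two arms (IV.A Analysis, repeated in IV.F).

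- **IV.A, Sample Size:** the target of 60, split 30 and 30, "was chosen to allow detection of a 35% difference between the LM-DA and control arms". The table beside it is for 80% power and alpha 0.05.
- **IV.F, Data Analysis Plan:** the same 60, again split 30 and 30, was "chosen to allow detection of a 30% difference between the LM-DA and control arms".
- **IV.C, Study Design:** "Thirty nine patients will be randomized to the LM-DA group, while 21 will be randomized to the control group".

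IV.A defends the planning difference in three ways. It reports that "In a prior small study, 62% of parents of at-risk youth who received LMC reduced home" access to firearms, against 0% without counselling. It states that "Estimates for the effect of LMC on behavior among adults with suicide risk do not exist". It then concludes that "our assumption of a 35% difference is conservative (prior work with other DAs has found an effect size of 40-80% on DCS between groups", citing reference 92. The description of the DCS earlier in IV.A cites the same reference for a different statement: the "DCS has been shown to discriminate between known groups who make or delay decisions (effect size 0.4-0.8").

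**The concern.** One sample size cannot have been chosen for two different detectable differences with the same power, alpha and allocation. The two sections are otherwise almost identical, so a reader of IV.F alone has no warning. That reader would take a null primary result as fairly strong evidence against a 30-point effect, when the design would miss such an effect about a third of the time.

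The allocation adds to this. Both sample-size statements assume equal arms, but the design section does not use equal arms, and an unequal split of the same total has less power in these scenarios.

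Finally, calling 35 points conservative tells readers that the true effect is probably larger. If the evidence behind the word does not concern the primary measure, that reassurance has no basis in the plan.

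**Working it through.** **Inputs.** Power 80%, alpha 0.05, N = 60 and the table rows come from IV.A; the 39/21 split comes from IV.C. The control column of the table is broken in the text, so I take control rate = LM-DA rate minus difference. The 20% control rate is inferred in this way. Sidedness and the test for the two-arm comparison are not stated; a two-sided test with the pooled-variance formula and no continuity correction reproduces the table.

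**Step 1: reproduce the table.** With p̄ the mean of p1 (control) and p2 (LM-DA), patients per arm are

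n = [1.960·√(2p̄(1−p̄)) + 0.842·√(p1(1−p1) + p2(1−p2))]² / (p2−p1)²

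- 0.30 vs 0.65: (1.3842 + 0.5567)² / 0.1225 = 30.75, so 31 per arm, total 62.
- 0.30 vs 0.60: (1.3790 + 0.5646)² / 0.09 = 41.97, so 42 per arm, total 84.

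| Difference | Control vs LM-DA | Computed total | Table |
|---|---|---|---|
| 35 points | 0.50 vs 0.85 | 54 | 54 |
| 35 points | 0.30 vs 0.65 | 62 | 62 |
| 35 points | 0.20 vs 0.55 | 58 | 58 |
| 30 points | 0.50 vs 0.80 | 78 | 78 |
| 30 points | 0.30 vs 0.60 | 84 | 84 |
| 30 points | 0.20 vs 0.50 | 78 | 78 |

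The table is therefore correct as a 1:1 calculation. Its damaged first row shows only 0.6 and 64. The same formula for 0.60 vs 0.90 gives (1.2002 + 0.4835)² / 0.09 = 31.50, so 32 per arm, total 64. That row is thus consistent with a further 30-point case, and the table's full 30-point range is probably 64 to 84. Every 30-point case needs more than 60.

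**Step 2: power with 60 patients.** With q the pooled rate weighted by arm size,

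power = Φ[(Δ − 1.960·s0) / s1], s0 = √(q(1−q)(1/nC + 1/nT)), s1 = √(p1(1−p1)/nC + p2(1−p2)/nT)

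Worked case, 0.30 vs 0.60:

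- 30/30: q = 0.45, s0 = 0.1285, s1 = 0.1225; (0.30 − 0.2518)/0.1225 = 0.394; power 65.3%.
- 39/21: q = (21×0.30 + 39×0.60)/60 = 0.495, s0 = 0.1353, s1 = 0.1271; (0.30 − 0.2652)/0.1271 = 0.274; power 60.8%.

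| Control rate | 35 points, 30/30 | 35 points, 39/21 | 30 points, 30/30 | 30 points, 39/21 |
|---|---|---|---|---|
| 20% | 81.6% | 77.1% | 69.2% | 63.4% |
| 30% | 79.0% | 75.1% | 65.3% | 60.8% |
| 50% | 84.3% | 82.2% | 69.2% | 67.0% |

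For 0.60 vs 0.90, power is 78.0% at 30/30 and 76.8% at 39/21. Exact enumeration of the uncorrected chi-square test on the 20%, 30% and 50% rows at 30/30 gives 69.2%, 66.3% and 69.2% for 30 points, so the approximation is adequate.

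**Step 3: the support for 'conservative'.** Each item is set against the primary measure.

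- 62% vs 0%: home firearm access, reported by parents of at-risk youth. This is another outcome and another population.
- No estimates exist for at-risk adults: an absence of data cannot make a chosen value cautious.
- 40-80% on the DCS: the metric is not stated. It could be a difference in the proportion below 25, a relative change, or a standardised effect written as a percentage. The plan does not say which.

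**The case against.** The strongest reply is that this is a feasibility-driven pilot, that 35 points does match the table, and that IV.F merely carries a stray figure. Most of this stands. The sample size was set with feasibility in mind, n = 60 is reasonable for 35 points at 30/30, and nothing here requires more patients. It is also fair that 35 is below both quoted comparators (62 and 40-80), so 'conservative' may only mean smaller than the effects cited. That reading still needs those effects to be on the same scale as the primary measure, which the documents do not show. The stray figure does need correcting, because it sits in the analysis plan and overstates what the design can detect.

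Three stronger readings are tempting and are not supported.

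- **That reference 92 is misquoted.** A reader might infer that the 0.4-0.8 between people who make and people who delay decisions was turned into 40-80% for decision aids. One source could report both results, and it cannot be consulted here.
- **That 35 points exceeds anything the cited effect sizes imply.** Turning 0.4-0.8 into percentage points needs a score distribution, which the documents do not give. Table 1's "Effect size 0.3-0.4 after intervention (target score <25") does not settle it, because its metric is also unstated.
- **That 30 points always needs 18 to 24 more patients.** This holds for the three legible rows (78 − 60 = 18; 84 − 60 = 24). If the damaged row is 0.60 vs 0.90, its gap is only 64 − 60 = 4.

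**Conclusion.** The inconsistency is real and the 30-point statement in IV.F is wrong as written. At the 30/30 split that IV.F itself states, power for 30 points is 65-69% for control rates of 20-50%, and 78% at a control rate of 60%. It is below 80% in every 30-point case the table appears to cover. At 30/30 the 35-point statement in IV.A is sound to within a point (79-84%). Under the 39/21 split in IV.C, power for 35 points is 75-82% and for 30 points 61-67%, and no sample-size statement acknowledges this.

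'Conservative' is unsupported rather than refuted.

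These figures assume a two-sided 5% chi-square test without continuity correction and no missing primary data; the plan expects little. A different test would need its own figures. The consequence is a misstated design justification, not an invalid analysis or an inadequate pilot.

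**What to change.** 1. Reconcile 30% with 35%, and 30/30 with 39/21, across IV.A, IV.C and IV.F. Which allocation is meant is for the sponsor to settle.
2. Put one identical sentence in IV.A and IV.F. If the split is 30/30: *With 30 patients per arm (two-sided 5%, chi-square without continuity correction), power is 79-84% for a 35-point and 65-69% for a 30-point difference in DCS <25, for control rates of 20-50%.* If it is 39/21, state 39 and 21 patients and use 75-82% and 61-67%.
3. Delete 'conservative' and describe 35 points as a planning value set with pilot feasibility in mind, unless the source reports a difference in the proportion with DCS <25. If it does, state that metric and the groups compared.

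The cost is wording in two sections, plus whatever IV.C needs once the allocation is settled. The total of 60, the primary measure and the primary analysis stay as they are. The downside is that the stated power for 30 points becomes less favourable.

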- ED Providers: Provider survey invitations will be emailed and will include a unique link to complete a REDCap online survey. To supplement these survey data, we will conduct qualitative interviews with 20 ED providers to further explore LM-DA acceptability, feasibility of real-world implementation, and training. All providers who are a part of a patient –subject’s clinical team will be invited by email to participate in the initial survey. At the end of the survey, there will be an invitation to participate in a follow-up qualitative interview. Interested providers will be instructed to email or call the study team, as their name will not be on the survey. If more providers opt for qualitative surveys than anticipated, we will select a sample to optimize balance across provider groups and sites.
- All participants will receive a gift card as an incentive (\$25 for patients; \$10 for family or friends; \$5 for providers who complete the online survey; \$15 for providers who complete a qualitative interview for a total incentive of \$20).

Randomization:

- Patients: At each ED, enrolled patients will be randomly assigned to the LM-DA or control arm (Figure 2). To reduce bias and achieve balance among arms, we will randomize patients in blocks.⁹⁰
- Family members/friends: If a family member or friend is concurrently enrolled, they will be automatically randomized into the same arm as the patient, as they will potentially be reviewing the LM-DA with the patient and assisting with decision making.
- ED Providers: Providers will be asked to provide answers to a survey after the patient’s visit. Thus, they are not randomized, nor can they feasibly be blinded given their ongoing care relationship with patients during the study.

Baseline Measurements & Intervention:

- Patients: The RA will give the patient a study tablet with an introductory short survey and basic information about suicide prevention. In the intervention arm only, patients will then complete the LM-DA on the tablet. All patients in both arms will answer questions about their ED care and their anticipated care plan (including knowledge about the rationale for reducing access to firearms as a safety measure, and their intent to decrease access to firearms at home). Study participation will not affect clinical care, including discharge or admission planning.

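### The sample size is justified for 30 versus 30 patients but the design randomises 39 versus 21, and the same n=60 is tied to two different target differences (35% and 30%)

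*Combined protocol and SAP*

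**What the plan says.** - **IV.A, Sample Size.** The target of 60 is described as "30 LM-DA and 30 control) was chosen to allow detection of a 35% difference between the LM-DA and control arms for the primary measure", which is DCS <25. The accompanying table (headed Table 5, called Table 2 in the text) gives total sample sizes for 80% power at alpha 0.05.
- **IV.C, Study Design and Research Methods.** The total is again 60, but "Thirty nine patients will be randomized to the LM-DA group, while 21 will be randomized to the control group (13/7 at each site".
- **IV.C, Randomization.** "To reduce bias and achieve balance among arms, we will randomize patients in blocks". No ratio or block size is given here.
- **IV.F, Data Analysis Plan.** The sizing statement returns with a different target: "our target sample size (n=60; 30 LM-DA and 30 control) was chosen to allow detection of a 30% difference between the LM-DA and control arms".

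No passage in the available text explains the 13:7 ratio or reconciles it with 30 per arm. Figure 2, which shows the study flow, is not visible.

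**The concern.** There are two separate contradictions, both in current text.

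The first is the allocation. A randomisation list cannot satisfy both 30/30 and 39/21. The unequal version is not a slip in one digit: 3 × 13 = 39, 3 × 7 = 21, and 39 + 21 = 60.

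The second is the target difference. The same 60 patients are said to have been chosen for 35 points in one section and for 30 points in another. With the other planning values unchanged, one sample size cannot have been derived for both.

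At stake are which allocation is implemented and whether the stated power applies to the primary between-arm comparison. The trial also commits to CONSORT reporting, which calls for one allocation ratio and one sample-size rationale.

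**Working it through.** **Inputs.** From the sample size table: 80% power and alpha 0.05. Sidedness is not stated; two-sided reproduces the table. From IV.A and IV.F: 30 versus 30. From IV.C: 39 LM-DA versus 21 control. No inflation for dropout is stated.

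**Control rates.** The table is broken in the text available. A control rate of 0.5 is printed where it fits. A 0.3 is printed, but beside an LM-DA rate of 0.5 and a difference of 0.3, where it does not fit. The rates 0.3 and 0.2 used below are therefore LM-DA rate minus difference. A fragment showing 0.6 and 64 fits 0.6 versus 0.9, so a fourth control rate of 0.6 is possible.

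**Step 1: reproduce the table.** The pooled two-proportion formula at 1:1 is

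n per arm = [1.96 √(2 p̄(1−p̄)) + 0.8416 √(p₀(1−p₀) + p₁(1−p₁))]² / (p₁−p₀)²

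For 0.5 versus 0.85, p̄ = 0.675 and n = 26.9, rounded up to 27 per arm, or 54 in total. The table says 54. All eight legible rows match:

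| Control | Total N for 30 points | Total N for 35 points | Total N for 40 points |
|---|---|---|---|
| 0.5 | 78 | 54 | 40 |
| 0.3 | 84 | 62 | 48 |
| 0.2 | 78 | 58 | not legible |

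For 0.6 versus 0.9 the formula gives 64, matching the fragment. One-sided, continuity-corrected and unpooled versions give 44, 66 and 50 for 0.5 versus 0.85, so they do not fit. The table is a two-sided 1:1 calculation.

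**Step 2: power of 60 patients under each allocation.**

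Power = Φ{[(p₁−p₀) − 1.96 s₀] / s₁}, where s₀ = √(p̄(1−p̄)(1/n₀+1/n₁)), s₁ = √(p₀(1−p₀)/n₀ + p₁(1−p₁)/n₁), and p̄ is weighted by arm size.

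Worked case, 0.3 versus 0.65 at 21 control and 39 LM-DA: p̄ = 0.5275, s₀ = 0.1351, s₁ = 0.1258. Then (0.35 − 1.96 × 0.1351)/0.1258 = 0.677, and power is 75.1%.

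| Control | 35 points, 30/30 | 35 points, 39/21 | 30 points, 30/30 | 30 points, 39/21 |
|---|---|---|---|---|
| 0.5 | 84.3% | 82.2% | 69.2% | 67.0% |
| 0.3 | 79.0% | 75.1% | 65.3% | 60.8% |
| 0.2 | 81.6% | 77.1% | 69.2% | 63.4% |
| 0.6 (possible) | 92.2% | 90.8% | 78.0% | 76.8% |

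Exact enumeration of the uncorrected chi-square test at 39/21 gives, for control 0.5, 0.3 and 0.2, 83.4%, 75.2% and 77.4% at 35 points and 67.6%, 61.2% and 64.0% at 30 points. These are within about 1 point of the formula.

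**Step 3: what 60 patients can detect at 80% power.** For control 0.5, 0.3 and 0.2: 33.4, 35.4 and 34.3 points at 30/30; 34.2, 37.0 and 36.2 points at 39/21. For control 0.6 it is about 31 points either way.

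**Step 4: total needed at 13:7 for 80% power** (before rounding up by arm). For control 0.5, 0.3 and 0.2: 56.6, 67.3 and 64.2 patients for 35 points; 82.0, 92.4 and 85.9 for 30 points.

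**The case against.** The strongest reply is that this is a pilot. Its stated purpose is acceptability, feasibility and preliminary effects, and the Table 1 progression criteria do not require a significant between-arm test. A loss of 2 to 4.6 power points matters little in that setting. This stands as far as the size of the allocation effect goes. It does not excuse two incompatible randomisation schemes, and the protocol does name a primary measure, a between-arm primary analysis and an 80% power basis.

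Four narrower points also stand:

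- At 35 points, the split alone carries power across 80% only at control 0.2, which is an inferred rate. At 0.3, power is already just short at 30/30 (the table asks for 62). At 0.5 it stays above 80%.
- The plan does not name the test for the arm comparison. Under Fisher's exact test, power at 35 points for control 0.5, 0.3 and 0.2 is 77.7%, 71.4% and 73.8% at 30/30, and 78.8%, 68.4% and 71.5% at 39/21. On that test no case reaches 80%, and at control 0.5 the unequal split is not the worse one.
- The 30-point shortfall depends on the control rate. At 0.65 versus 0.95, the same formula gives 84.6% at 30/30 and 83.7% at 39/21. The protocol commits to no single expected control rate, so the firmest form of the criticism is the comparison with its own table.
- No calculation in the table is wrong. The fault is inconsistency between sections.

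**Conclusion.** The concern holds. The allocation conflict and the two target differences are in the current text, and nothing visible reconciles them. The published sample sizes are for 1:1 allocation and do not describe the 39/21 design.

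The allocation effect on power is modest: at 35 points and control rates 0.2 to 0.5, the range moves from about 79-84% to about 75-82%. The 30-point statement in IV.F is the more serious numerical fault. The table requires 78, 84 and 78 patients in its legible 30-point rows (64 in the damaged one), all above 60.

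The power figures assume a two-sided pooled comparison of proportions, no missing data, and control rates partly inferred from a damaged table. The contradictions themselves depend on none of these assumptions. The correction is needed because the allocation must be unambiguous before patients are randomised.

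**What to change.** State one allocation and one target difference in IV.A (Sample Size), IV.C (Study Design) and IV.F, and give the ratio in the Randomization text.

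- **If 39/21 is the design:** recompute the table at 13:7, give the reason for the unequal ratio, and state about 75-82% power for 35 points at control rates 0.2 to 0.5 (80% power for about 34 to 37 points).
- **If 30/30 is the design:** change IV.C to 30/30, that is 10/10 at each site, and state about 79-84% power for 35 points.
- **In either case:** replace the 30% in IV.F with the difference that 60 patients support, or state that power for 30 points is about 65-69% (30/30) or 61-67% (39/21). Name the test for the arm comparison, since the power statement depends on it. If 0.6 is one of the planning control rates, include its figures.

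The cost is a wording change in these sections and one recalculation, with no extra patients. If 39/21 is kept, the stated power becomes slightly less favourable.
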